1. SYNOPSIS

Name of Sponsor: MediciNova Inc.

Name of Investigational Product: MN-001

Title of Study: A Randomized, Placebo-Controlled, Double-Blind Six Month Study Followed by an Open-Label Extension Phase to Evaluate the Efficacy, Safety, and Tolerability of MN-001 in Subjects with Idiopathic Pulmonary Fibrosis

Study Center(s): Single center

Phase of Development: 2a

Study Objectives

Primary Objectives:

The primary objectives are to evaluate:

- the effect of MN-001 in subjects with idiopathic pulmonary fibrosis (IPF) on the absolute and relative change from baseline of FVC and FVC % predicted up to 26 weeks
- the effect of MN-001 in subjects with idiopathic pulmonary fibrosis (IPF) on the semiannual rate of decline of disease activity based on forced vital capacity (FVC)

Secondary Objectives:

The secondary objectives are to evaluate:

- the safety and tolerability of MN-001 in subjects with IPF
- Semiannual rate of decline on disease activity based on the 6-minute walk test (6MWT)
- Change from baseline on disease activity based on Modified Medical Research Council Dyspnea Score (MMRC)
- Change from baseline on quality of life (QOL) measured by A Tool to Assess Quality of Life in Idiopathic Pulmonary Fibrosis (ATAQ-IPF)
- Frequency of worsening IPF
- Time to first worsening IPF

METHODOLOGY

This is a randomized, placebo-controlled, double-blind, 6-month study followed by a 6 month open-label extension phase to evaluate the efficacy, safety, and tolerability of MN-001 in IPF patients. MN-001 1500 mg to be administered as 750 mg bid or 500 mg tid, or matching placebo will be orally administered over a 26-week period in subjects with a confirmed diagnosis of IPF per the American Thoracic Society (ATS) 2011 Guidelines (Raghu et al 2011). Approximately 15 subjects are planned to be enrolled. This study will consist of two treatment arms, MN-001 and matching placebo. Randomization will occur in a 2:1 ratio (MN-001: placebo). Eligible subjects will consist of males and females ranging in age from 21 to 80 years old, inclusive.

The study will consist of a Screening Phase (up to 3 months prior to Day1) followed by a 26 week double-blind Treatment Phase, a 26 week Open-Label Extension (OLE) phase and a Follow-up Visit (within 4 weeks after the last dose).

Screening Phase (up to 3 months prior to Day 1)

During the Screening Phase, subjects will be assessed for study eligibility. The following assessments will be performed: medical history including review of prior medications, physical examination including height and body weight, vital signs and an electrocardiogram. Clinical labs, chemistry (including liver enzymes and fasting lipid profile), hematology, urinalysis and a serum pregnancy test will be collected as well as serum lysyl oxidase-like 2 levels (LOXL2), a biomarker for IPF.

Double-blind Treatment Phase (26 weeks)

Subjects who complete all of the screening assessments and meet all inclusion/exclusion criteria will be started on MN-001 1500 mg to be administered as 750 mg bid or 500 mg tid, or matching placebo. Subjects will return to the clinic on Treatment Day 1 to receive their first dose of study medication. Subsequently, subjects will return to the clinic on a regular basis (see Table 1 Schedule of Assessments) for 26 weeks. Subjects participating in the study will return to the clinic Month 1 and every 3 months for evaluation. During the Treatment Phase, safety and efficacy parameters will be assessed and concomitant medications will be documented. The safety and tolerability of MN-001 will be evaluated by an Independent Safety Monitor during this phase.

Open-Label Extension (OLE) Phase (26 weeks)

Upon completion of the Double-blind Treatment Phase, subjects who were taking placebo, will participate in the open-label extension (OLE) phase for an additional 6 months. Subjects who were in the placebo group will be administered MN-001 750 mg bid or 500 mg tid for the remainder of the OLE Phase.

Subjects randomized to the MN-001 group will continue the study drug for additional 6 months. All subjects will return to the clinic for evaluation at 1 month and every 3 months after the start of the open-label extension phase (Months 7, 9 and 12).

Individual Stopping Criteria

Subjects who experience an adverse event of Grade 2 nausea and/or diarrhea for greater than 3 consecutive days or Grade 3 nausea and/or vomiting for greater than 1 day thought to be related to study drug will be discontinued from the study. Additionally, subjects who experience an adverse event of Grade 3 abdominal pain lasting for greater than 1 day thought to be related to study drug will be discontinued from the study.

Study Stopping Rules

The study will be stopped if two subjects experience a Grade 4 adverse event thought to be related to study drug.

Follow-up Phase

All subjects who complete the study will return for a follow-up visit (within 4 weeks from last dose) to assess adverse event status and to document concomitant medications.

Number of Subjects (Planned): The number of subjects planned for this study is approximately 15.

Study Entry Criteria:

Inclusion Criteria:

- Male or female subjects ages 21 to 80, inclusive
- Presence of IPF confirmed per ATS criteria (2011)
- Presence of disease, stage I-III defined by GAP index (Gender, Age and Physiology)
- Subjects who are currently treated with OFEVTM (Nintedanib) should be on a stable dose for at least 3 months prior to initiation of the study drug.
- Females of child-bearing potential must have a negative serum β-hCG at screening and must be willing to use appropriate contraception (as defined by the investigator) for the duration of study treatment and 30 days after the last dose of study treatment.
- Males should practice contraception for the duration of study treatment and 30 days after the last dose of study treatment as follows: condom use and contraception by female partner.
- Subject is in stable condition on the basis of medical history, physical examination, and laboratory screening, as determined by the investigator.
- Subject is willing and able to comply with the protocol assessments and visits, in the opinion of the study nurse/coordinator and the Investigator.
- Written informed consent is obtained prior to participating the study.

Exclusion Criteria:

- Expected to receive a lung transplant within 1 year from the start of the Treatment Phase or on a lung transplant waiting list at the start of the Treatment Phase.
- Known explanation for interstitial lung disease
- Subjects on OFEVTM (Nintedanib) with a dose interruption due to significant adverse events within 6 weeks of screening visits.
- Ongoing IPF treatments with investigational therapy
- Ongoing IPF treatments with Esbriet® (Pirfenidone)
- Immunosuppressants (i.e., Mycophenolate, Imuran, Cyclophosphamide), and cytokine modulating agents within 1 month of Screening Visit and throughout the study
- Use of antibiotics and systemic steroids due to IPF exacerbation within 1 month of Screening Visit
- Clinically significant cardiovascular disease, including myocardial infarct within last 6 months, unstable ischemic heart disease, congestive heart failure or angina
- Resting pulse < 50 bpm, SA or AV block, uncontrolled hypertension, or QTcF > 450 ms
- Immune system disease
- Any significant laboratory abnormality which, in the opinion of the Investigator, may put the subject at risk
- History of malignancy < 5 years prior to signing the informed consent, except for adequately treated basal cell or squamous cell skin cancer or *in situ* cervical cancer.
- History or evidence of drug or alcohol abuse
- History of HIV (human immunodeficiency virus) or other active infection.
- Currently has a clinically significant medical condition including the following: neurological, psychiatric, immunological, metabolic, hepatic, hematological, pulmonary (other than IPF), cardiovascular (including uncontrolled hypertension), gastrointestinal, urological disorder, or central nervous system (CNS) infection that would pose a risk to the subject if they were to participate in the study or that might confound the results of the study.

Note: Active medical conditions that are minor or well-controlled are not exclusionary if, in the judgment of the Investigator, they do not affect risk to the subject or the study results. In cases in which the impact of the condition upon risk to the subject or study results is unclear, the Medical

Monitor should be consulted.

- CYP2C8 and CYP2C9 substrates with narrow therapeutic indices (i.e. paclitaxel, phenytoin and S-warfarin) within 14 days of Screening Visit and throughout the study.
- Macrolide or quinolone class antibiotics within 14 days of Screening Visit and throughout the study.
- Poor peripheral venous access that will limit the ability to draw blood as judged by the Investigator.
- Currently participating, or has participated in, a study with an investigational or marketed compound or device within 3 months prior to signing the informed consent.
- Unwilling or unable to conduct Spirometry (Vital Capacity) test.
- Unable to cooperate with any study procedures, unlikely to adhere to the study procedures and keep appointments, in the opinion of the Investigator, or is planning to relocate during the study.

Investigational Product, Dosage and Mode of Administration: Three MN-001 tablets (750 mg) or matching placebo to be administered orally twice daily or two tablets (500 mg) or matching placebo to be administered three times daily for a total daily dose of 1500 mg.

Duration of Treatment: approximately 12 months/52 weeks

Reference Therapy, Dosage, and Mode of Administration: matching-placebo

Criteria for Evaluation

Efficacy Endpoints:

Efficacy will be assessed by the following:

- FVC and FVC% predicted up to 26 weeks
- Semiannual decline on disease activity based on forced vital capacity (FVC)
- Annual/semiannual decline on disease activity based on the 6-minute walk test (6MWT)
- Modified Medical Research Council Dyspnea Score (MMRC)
- Quality of life (QOL) measured by A Tool to Assess Quality of Life in Idiopathic Pulmonary Fibrosis (ATAQ-IPF)
- Frequency of worsening IPF
- Time to first worsening IPF

Safety Endpoints:

The proportion of subjects with:

- Treatment-emergent adverse events (TEAEs)
- Treatment-emergent serious adverse events (TESAEs)
- Treatment discontinuations due to treatment-emergent adverse events

Additional Safety Endpoints:

• Laboratory measures (chemistry, hematology, urinalysis), vital signs, and 12 lead-electrocardiograms (ECGs).

Sample Size Justification

No prior data are available on which to base assumptions for sample size/power considerations. The results of this pilot study will be used to design future studies, and the sample size of approximately 15 subjects is deemed to be appropriate for this purpose.

Table 1: Schedule of Events

Phase	Scree	ening		1	Double-Bli	ind Treatn	nent	ont Open-Label Extension Follow -up End of Study			Open-Label Extension				Early Lab Termination ^c retest ^f	
	Day -90 to -8	Day -7 (±5d)	Day 1	Week 1 (±3d)	Month 1 (±5d)	Month 3 (±5d)	Month 4 (±5d)	Month 6 (±5d)	Week 27 (±3d)	Month 7 (±5d)	Month 9 (±5d)	Month 10 (±5d)	Month 12 (±5d)	Month 13 (±5d)		
Visit Type	Clinic	Clinic	Clinic	Tel	Clinic	Clinic	Tel	Clinic	Tel	Clinic	Clinic	Tel	Clinic	Clinic		
Study Visit Number	1	2	3	4	5	6	7	8	9	10	11	12	13	14	ET	LRT
Informed consent	X ^{a b}	X^{b}														
Inclusion/exclusion criteria review		X	X													
Medication history		X														
Physical Examination		X			X	X		X		X	X		X	X	X	
Body height		X														
Body weight		X			X	X		X		X	X		X	X	X	
Vital signs (sitting)		X	X		X	X		X		X	X		X	X	X	
12-lead ECG		X	Xg		X	X		X		X	X		X		X^{d}	
CBC/CMP, CK, UA Fasting lipid panel		X			X	X		X		X	X		X		X^{d}	X
Serum pregnancy test		X														
Urine pregnancy test			X		X	X		X		X	X		X		X^{d}	
Pulmonary function		X				X		X			X		X		X^{d}	
6 minute-walk test		X^h				X^h		X^h			X		X		X^{d}	
ATAQ-IPF		X				X		X			X		X		X^{d}	
MMRC		X			X	X	X	X		X	X	X	X		X^{d}	
Plasma for Biomarker		X						X					X		X^{d}	
Adverse event review			X	X	X	X	X	X	X	X	X	X	X	X	X	X
Concomitant med review			X	X	X	X	X	X	X	X	X	X	X	X	X	X
Study Drug Dispensing			X		X	X		Xe		X	X		X			
Dispense/Review/ Collect Patient Diary			X		X	X		X		X	X		X		X	
Study Drug Accountability		f (ICE	'11.1		X	X		X		X	X		X		X	

a. A copy of the informed consent form (ICF) will be given to the patient for review.

b. Signing of the ICF will occur during screening phase (Visit 1 or Visit 2) prior to conducting any study assessments.

c. Assessments to be done for early termination for any reason. Other assessments/procedures to be done at PI discretion, if necessary.

d. Assessments do not need to be performed if prior assessments were within one month of this early termination visit.

MediciNova Inc.

Final Protocol MN-001-IPF-201

Amendment 2 December 21, 2015

- e. Dispense Open-label study medications after all procedures and assessments have been completed. f. Lab retest assessments to be done for subjects with clinically significant abnormal lab findings. g. 12-lead ECG to be done at Hour 1.5 (\pm 30 minutes) post dose h. The 6 minute walk test should be performed twice during these visits.

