8.8.1.1. Screening Phase (Up to 3 months prior to Day 1)

Visit 1 (Day -90 to Day -8)

At any point during this time, subject may be approached for participation in the study. An informed consent form (ICF) will be given to the subject and the subject will be instructed to read the ICF and ask the study staff any questions they may have. The subject can either sign the ICF then or defer signing until they return for Study Visit 2.

Visit 2 (Day- 7 ± 5 days)

During the Screening Phase, once the informed consent form is signed, the following assessments will be performed/collected):

- Inclusion/Exclusion criteria review
- Medical history
- Physical examination
- Height/body weight
- Vital signs including supine blood pressure, respiratory rate, heart rate, and temperature
- 12 lead Electrocardiogram (ECG)
- Fasting safety labs chemistry (including CPK, liver enzymes, lipid panel) hematology, and urinalysis labs

- Serum β-hCG (pre-menopausal females)
- Blood Sample for biomarker
- Prior/concomitant medication review
- Pulmonary function test
- 6 minute-walk test (6MWT)*
- Dyspnea score (MMRC: Modified Medical Research Council Dyspnea Score)
- ATAQ-IPF (A Tool to Assess Quality of Life in IPF)

The results of pulmonary function test, 6MWT, MMRC and ATAQ-IPF at this visit are considered "Baseline" values.

* Two tests should be performed for 6MWT

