8.8.1.2. Double-Blind Treatment Phase (26 weeks)

Subjects will enter the clinic in the morning prior to breakfast. Once the pre-dose fasting labs have been completed, subjects will be given breakfast except on Baseline Day 1.

Baseline Clinic Visit: Day 1

The following assessment will be done:

- Inclusion/Exclusion criteria review
- Vital signs including supine blood pressure, respiratory rate, heart rate, and temperature
- Urine β-hCG (in pre-menopausal females)
- Concomitant medication review
- Adverse event review
- Dispense study drug
- Dispense patient diary
- 12-lead ECG at Hour 1.5 (\pm 30 minutes) post dose

Once the pre-dose assessments have been completed, the subject will be administered the first dose of MN-001 (2 or 3 tablets of MN-001 250 mg) or matching placebo with water.

Clinic Visits: Months 1, 3 and 6* (± 5 days)

The following assessments will be done:

- Physical examination
- Body weight
- Vital signs including supine blood pressure, respiratory rate, heart rate, and temperature
- 12-lead ECG at Hour 1.5 (± 30 min) post dose

- Fasting safety labs chemistry (including CPK, liver enzymes, lipid panel) hematology, and urinalysis labs
- Urine β-hCG (pre-menopausal females)
- Blood Sample for biomarker (Month 6 only)
- Pulmonary function test (Months 3 and 6 only)
- 6MWT (Months 3 and 6 only)**
- Dyspnea score (MMRC)
- ATAQ-IPF (Months 3 and 6 only)
- Adverse event review
- Concomitant medication review
- Patient diary review
- Dispense study drug (Months 3 and 6 only)
- Study drug accountability
 - * Month 6 Clinic Visit is the start day (Day 1) of the Open-Label Extension (OLE) phase. All subjects will take MN-001 750 mg bid or 500 mg tid.
 - ** Two tests should be performed for 6MWT

Telephone Visits Week 1 (\pm 3 days) and Month 4 (\pm 5 days)

Between clinic visits, subjects will be called by a study team member (e.g., study coordinator or nurse) to collect information regarding their health status. The MMRC will be administered (only Month 4) and adverse events and concomitant medications will be documented.

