8.8.1.4 Follow-up / Laboratory Re-test Visits/ Early termination visit

Follow up clinic visit: Month 13 (\pm 5 days)

- Physical examination
- Body weight
- Vital signs including supine blood pressure, respiratory rate, heart rate, and temperature
- Adverse event review
- Concomitant medication review

Laboratory Re-test visit

Subjects who have clinically significant abnormal lab finding will return for a laboratory re-test visit and will have the following assessments performed:

- Fasting chemistry, hematology, or urinalysis lab, as indicated
- Adverse event review
- Concomitant medication review

Early Termination visit

Subjects who discontinued study medication will undergo the following assessments:

- Physical examination
- Body weight
- Vital signs including supine blood pressure, respiratory rate, heart rate, and temperature
- Adverse event review
- Concomitant medication review
- Patient diary review and collect
- Study drug accountability
- Study drug return
- 12-lead ECG**
- Fasting safety labs chemistry (including CPK, liver enzymes, lipid panel) hematology, and urinalysis labs**
- Urine β-hCG (pre-menopausal females)**
- Blood Sample for biomarker**
- Pulmonary function test**
- 6MWT**7
- Dyspnea score (MMRC)**
- ATAQ-IPF**
 - ** Assessment need not be performed if prior assessment occurred within 1 month of Early Termination Visit.

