13.1.4. Safety Analysis

Safety analyses will be conducted on the Safety Analysis Set.

The incidence of treatment-emergent AEs (TEAEs, defined as AEs occurring from the time of first dose through 7 days after the last dose of study medication), SAEs and AEs leading to discontinuations will be summarized by treatment group. Incidence of TEAEs will also be summarized by severity (mild, moderate, or severe), as well as by relationship to treatment (not related, possibly related, or probably related) and by seriousness.

Changes from baseline in laboratory values will be summarized by treatment groups for continuous variables. Lab shift tables showing incidence of new or worsening clinically significant findings from baseline to the last visit will be displayed by treatment groups. Shift from baseline to the highest lab value, and from baseline to the lowest lab value will also be displayed.

Incidence of out-of-normal-range values and markedly abnormal change from baseline in laboratory safety test variables will be tabulated by treatment group.

Changes in vital signs from baseline to each visit will be summarized by treatment groups.

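### The early-termination waiver accepts a pre-dose laboratory test, so a subject who stops before Month 1 can leave with no post-dose laboratory value

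*Protocol*

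**What the plan says.** Table 1 of the protocol lists the safety laboratory panel and the 12-lead ECG at the early-termination visit. Both carry footnote d: "Assessments do not need to be performed if prior assessments were within one month of this early termination visit". Section 8.8.1.4 gives the same rule, "Assessment need not be performed if prior assessment occurred within 1 month of Early Termination Visit", and marks with it the ECG and the "Fasting safety labs chemistry (including CPK, liver enzymes, lipid panel) hematology, and urinalysis labs". Neither place defines a month or asks that the earlier assessment come after the first dose. Physical examination, weight, vital signs, adverse event review and concomitant medication review are not waivable at that visit.

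The only pre-treatment panel is at the visit headed "Visit 2 (Day- 7 ± 5 days" in section 8.8.1.1. Day 1 has a post-dose ECG but no laboratory tests (Table 1, section 8.8.1.2). Week 1 is a telephone contact (section 6.2). Laboratory tests and ECG next appear at Month 1.

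The synopsis names laboratory measures and ECGs as additional safety endpoints. Protocol section 13.1.4 plans "Lab shift tables showing incidence of new or worsening clinically significant findings from baseline to the last visit", and SAP section 14.3 carries this out by phase and arm. SAP section 14.6 summarises ECGs by arm, phase and visit. The SAP has no rule for where an early-termination value goes in these tables.

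**The concern.** A waiver of this kind normally avoids repeating a test that already shows the subject's state on treatment. As written, it can be met by a test taken before treatment began. That can happen only in subjects who stop early, and some of those will stop because they did not tolerate the drug. One individual stopping criterion is "Grade 2 nausea and/or diarrhea for greater than 3 consecutive days", which can be met well before Month 1.

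Such a subject stays in the Safety Analysis Set, because that needs one post-dose safety assessment of any kind (SAP section 9). Yet the subject contributes no post-baseline laboratory change and no shift. The outputs then lack laboratory information on that subject, and nothing in the SAP would make the absence visible.

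**Working it through.** The plan states no figure on this point. The check is calendar arithmetic on the visit schedule.

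**Inputs**
- Visit 2 laboratory draw: Day -7 ± 5, so Day -12 to Day -2 (section 8.8.1.1).
- Day 1 ECG: 1.5 hours after the first dose (section 8.8.1.2).
- Month 1 visit: ± 5 days (section 8.8.1.2).
- Double-blind phase: 26 weeks × 7 = 182 days.
- About 15 subjects randomized 2:1: 15 × 2/3 = 10 on MN-001 and 15 × 1/3 = 5 on placebo.
- Assumption: one month is 30 days, with 28 and 31 as the range. Day numbering with and without a Day 0 is shown.

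**1. Laboratory tests, double-blind phase.** Last early-termination day on which the Visit 2 panel meets the waiver = Visit 2 day + one month (add 1 if there is no Day 0).

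| Month length | Visit 2 at Day -12 | Day -7 | Day -2 |
|---|---|---|---|
| 28 days | 16 (17) | 21 (22) | 26 (27) |
| 30 days | 18 (19) | 23 (24) | 28 (29) |
| 31 days | 19 (20) | 24 (25) | 29 (30) |

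With 30 days and a Day -7 draw, the limit is Day 23, and 23/182 = 12.6%. The ends of the Visit 2 window give 18/182 = 9.9% and 28/182 = 15.4%. A Month 1 visit held early in its window (from about Day 25 with a 30-day month) closes the gap sooner when Visit 2 was late.

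**2. ECG, double-blind phase.** Last day = Day 1 + one month = Day 31 (Day 29 to 32 over the range). Until the Month 1 visit, the only post-dose ECG can therefore be the Day 1 recording.

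**3. Laboratory tests, extension phase.** The Month 6 visit is the first day of the extension. Section 8.8.1.2 places fasting laboratory tests before dosing, and footnote e dispenses open-label drug after all procedures. SAP section 10.3 makes the pre-dose Month 6 values the baseline for former-placebo subjects. Their next panel is at Month 7, one month later. On nominal dates, the Month 6 panel can meet the waiver for the whole interval, so such a subject can stop with no laboratory value after a dose of MN-001. The timing of the Month 6 ECG relative to the first open-label dose is less clear, so no ECG claim is made here.

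**4. Effect on the tables.** SAP section 10.3 places default baselines at Visit 3, where no laboratory tests are scheduled. Under its general rule (closest value before the first dose), the Visit 2 panel is the laboratory baseline. A subject whose early-termination panel was waived then has a baseline and nothing after it. Each such MN-001 subject is 1/10 = 10% of that arm's subjects.

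**The case against.** **Other text encourages testing.** The waiver is permissive. Section 7.3 asks sites to try to complete the early-termination procedures. Footnote c allows further tests at the investigator's discretion. Section 8.8.2.12 requires enough information to establish an adverse event's outcome. Section 12.4 provides for laboratory measures where needed. This stands, so it would be wrong to call no testing the rule. But these clauses allow a test; none requires one or narrows the waiver. The follow-up visit does not help: it is for completers and has no laboratory tests or ECG.

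**The gap could be read as larger than it is.** A reader might count every day on which some waiver could apply and conclude that about half of each phase is affected. In the double-blind phase that count is 23 + 31 + 31 = 85 days on nominal visits, but 62 of them follow Month 1 or Month 3, when post-dose tests already exist. On those days the only issue is that the test may precede the event that led to stopping.

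**One subject is not 10% of the laboratory data.** With nine completers tested at Months 1, 3 and 6 and one early-termination panel, the waiver costs 1 of 9 × 3 + 1 = 28 post-baseline double-blind panels (3.6%). The stopper's later panels are lost through stopping, not through the waiver.

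**Frequency and direction are not known.** A reader might infer that early stops are likely and laboratory toxicity understated. Protocol section 4.2.1 reports that no gastrointestinal event led to discontinuation in the 4-week asthma study, and that no subject stopped for an adverse event in the 5-day study at 1500 mg/day. It reports eleven such discontinuations in an open-label study, without timing. The documents support possible, not likely, and a missing value has no known direction.

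**The ECG part is narrower.** The Day 1 ECG is already post-dose, so a first-dose condition changes nothing for it. Only a condition tied to the onset of the event would.

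**A required draw may be off drug.** The visit follows discontinuation, with no stated limit from the last dose. This stands: the remedy secures a post-dose value, not necessarily an on-drug one.

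**Conclusion.** The point holds for post-dose laboratory values in subjects whose early-termination visit falls in roughly the first two and a half to four weeks: about Day 18 to 28 with a 30-day month, and Day 16 to 30 over the month lengths and day numberings tried. It holds also for former-placebo subjects who stop between Months 6 and 7. For ECG, the claim is only that the single post-dose recording before Month 1 can be the Day 1 one.

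The two statements of the waiver agree, so this is a gap in the rule and not a contradiction. It affects few subjects at most. It matters because the arm has about 10 subjects, laboratory safety is a named endpoint, and the correction is small. The conclusion rests on the assumed length of a month and on a site that uses the waiver as written. It does not rest on any assumed rate of early stopping.

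**What to change.** **Protocol.** Amend footnote d and section 8.8.1.4 in two respects:
- The laboratory waiver can be met only by an assessment made after the first dose of study drug. For former-placebo subjects in the extension, this means after the first dose of MN-001, since their earlier panels followed placebo doses only.
- When the stop is for an adverse event, the laboratory and ECG waiver can be met only by an assessment made on or after that event's onset.

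**SAP.** In sections 14.3 and 14.6, state that the early-termination value is the last-visit value in the laboratory shift table and is included in the ECG summary. Flag its time since the last dose. Report by arm and phase how many subjects have no post-dose laboratory value and how many have no post-dose ECG.

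**Cost.** One blood draw and one ECG, both already listed for that visit, in the few subjects who stop early, plus short text changes. SAP version 1.0 is dated April 2021, and its section 6.3 describes randomization as done. If visits are complete, only the SAP part applies. It cannot recover a waived test, but it makes the missing values visible.
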